6.4. Study Intervention Compliance

When the individual dose for a participant is prepared from a bulk supply, the preparation of the dose will be confirmed by a second qualified member of the study site staff.

When participants are dosed at the site, they will receive study intervention directly from the investigator or designee, under medical supervision. The date and time of each dose administered in the clinic will be recorded in the source documents and recorded in the electronic CRF. The study treatment assignment and study participant identification will be confirmed at the time of dosing by a member of the study site staff other than the person administering the study intervention. Study site personnel will examine each participant's mouth to ensure that the study intervention was ingested.

6.5. Concomitant Therapy

Use of prescription or nonprescription drugs and dietary and herbal supplements are prohibited within 7 days or 5 half-lives (whichever is longer) prior to the first dose of study intervention. Limited use of nonprescription medications that are not believed to affect participant safety or the overall results of the study may be permitted on a case-by-case basis following approval by the sponsor. Acetaminophen/paracetamol may be used at doses of ≤ 1 g/day.

All concomitant treatments taken during the study must be recorded with indication, daily dose, and start and stop dates of administration. All participants will be questioned about concomitant treatment at each clinic visit.

Treatments taken within 28 days before the first dose of study intervention will be documented as a prior treatment. Treatments taken after the first dose of study intervention will be documented as concomitant treatments.

6.5.1. Rescue Medicine

There is no rescue therapy to reverse the AEs observed with PF-07059013; standard medical supportive care must be provided to manage the AEs.

6.6. Dose Modification

The decision to proceed to the next dose level of PF-07059013 (either an increase, decrease or repeat of previous dose level) will be made by the study team and the investigator based on safety, tolerability, and preliminary PK data obtained in at least 6 participants (at least 5 out of 6 actively treated participants and at least 1 placebo-treated participant) dosed at the prior dose level.

The dosing schedule may also be adjusted to add cohorts to evaluate additional dose levels. The study procedures for these additional participant(s)/cohort(s) will be the same as that described for other study participants/cohorts.

6.6.1. Dose Escalation and Stopping Rules

Dose escalation stopping rules will be used to determine whether the maximal tolerated dose has been attained. Dose escalation may be stopped if it is determined that the limits of safety and/or tolerability have been reached. This decision will be made after a discussion takes place between the sponsor study team and the investigator. The sponsor study team may not overrule the investigator's decision to stop dose escalation. If dose escalation is stopped because of any of these criteria, additional cohorts may receive the same or lower doses of the study intervention.

The dose escalation will be terminated based on the following criteria:

- If 50% or more of the participants receiving active drug at a given dose level (but not participants receiving placebo) develop similar clinically significant laboratory, ECG, or vital sign abnormalities (as described in [Appendix 8: Criteria for Vital Signs Abnormality](#)), in the same organ class, indicating dose-limiting intolerance.

- If post-treatment p50 values in 2 or more of the participants receiving active drug at a given dose level (but not participants receiving placebo), drops below 20 mmHg, in association with one or more of the following, in any of the respective participants:
 - Treatment emergent increase in EPO above the upper limit of reference range (Part 2 only).
 - Treatment emergent increase from baseline in absolute reticulocyte count, with magnitude of increase $\geq 250,000 / \mu\text{L}$ (Part 2 only).
 - Treatment emergent increase in lactate to above upper limit of normal.
- Severe nonserious AEs, considered as, at least, possibly related to study intervention administration, in 2 participants at a given dose level (but not participants receiving placebo), independent of within or not within the same system organ class, indicating dose-limiting intolerance.
- Dosing will be paused for any SAE that occurs in a participant receiving active treatment until causality is fully assessed by the PI and sponsor. Dosing may resume if the SAE is determined to be not drug-related by the PI and sponsor. If the SAE is determined to be either drug-related or unknown, either dosing will cease or the SAE will be evaluated by the sponsor's protocol review committee (or similar review group), which is independent of the study team and investigators. If the protocol review committee determines that dosing may resume, a plan that mitigates risks to participants with the resumption of dosing will be implemented. Such a plan could include a revision of inclusion/exclusion criteria, repeating or reducing the dose, or adding appropriate safety monitoring.
- It is determined that the limit of safety and/or tolerability has been reached. This decision will be made following discussions between the study team and the investigator.
- Other findings that, at the discretion of the study team and investigator, indicate that dose escalation should be halted.
- If, at any dose level, the average exposure reaches or exceeds the PK stopping limits: unbound plasma $C_{\text{max}} = 1.5 \mu\text{g}/\text{mL}$ or unbound plasma $AUC_{24} = 22.5 \mu\text{g}\cdot\text{hr}/\text{mL}$.
- If, based on the observed data, the group mean of unbound plasma C_{max} or AUC of the next planned dose is projected to exceed the escalation limits, that dose will not be explored. Modified doses may be explored if they are not expected to exceed PK stopping criteria.

Progression to the next dose will occur if the last dose was well tolerated and after satisfactory review of the available safety and PK data.

For Part 1, each dose escalation will be based on review of lactate and p50 data up to at least 8 hour post dose and all other safety data up to a minimum of 72-hours post dose plus PK assessments up to 24-hours post dose, in at least 5 out of 6 actively treated participants and at least 1 placebo-treated participant dosed in the previous dose level.

For Part 2, each dose escalation will be based on review of EPO and lactate data up to at least Day 7, reticulocyte and p50 data up to at least Day 14, and all other safety data up to Day 15 plus PK assessments up to Day 8, in at least 5 out of 6 actively treated participants and at least 1 placebo-treated participant dosed in the previous dose level.

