Visit Identifier ^a	Screening	Treatment Phase (all activities at 0H (predose) unless otherwise specified)																		Follow-up ^b		E/T		
		Days Relative to Day 1	-28 to -2	-1	1 ^j	2	3	4	5	6	7 ^j	8	9	10	11	12	13	14 ^j	15	16	17	18	Visit: 21±1	Contact: 42-49
CCI [REDACTED]																								

- a. **Visit Identifier:** Day relative to start of study treatment (Day 1).
- b. **Follow-up:** Onsite follow-up visit to occur between Day 20 to Day 22. Follow-up contact may occur via telephone and must occur 28 to 35 days from administration of the final dose of investigational product (ie, Day 42 to Day 49).
- c. **Physical Examination:** Complete physical examination will be conducted at Screening or upon admission (Day -1). Brief physical examination may be performed at other times, as appropriate, for findings during previous examination or new/open AEs, at investigator's discretion.
- d. **12-lead ECG:** Single at Screening, and triplicate at all other timepoints.
- e. **Supine blood pressure:** Where orthostatic blood pressure assessment will be conducted, supine blood pressure does not need to be repeated separately.
- f. **Study Treatment Administration:** Refer to [Section 6.1.1](#) and [Section 5.3.1](#).
- g. **Safety laboratory:** Participants should fast for at least 4 hours prior to sample collection, except 8 hours postdose sample. Only chemistry panel is required for 8 hours postdose.
- h. **Lactate, EPO, Reticulocytes:** Unless needed for screening, review of data is not required prior to dosing but lactate and EPO data up to at least Day 7, and reticulocyte data up to at least Day 14 will be reviewed prior to dose escalation. Refer to [Section 6.6.1](#) for details.
- i. **Pharmacokinetics:**
For dosing days - Samples will be collected predose, *where applicable*. For Day 1, 7 and 14, refer to [C List of Procedures for Part 2 Study Day 1, 7 and 14](#).
For post last dose - Day 15 samples will be collected 24H and 36H post last dose, Day 16 to 18 samples will be collected 48H, 72H and 96H post last dose respectively.
j. **Day 1, 7 and 14:** Refer to [C List of Procedures for Part 2 Study Day 1, 7 and 14](#) for details.
k. **Day 4 and 10:** PK samples, 12-lead ECG, supine blood pressure and pulse rate will be taken at predose and 8 hours postdose.
[REDACTED]

C. List of Procedures for Part 2 Study Day 1, 7 and 14

Hours Post dose	0 ^a	0.5	1	2	4	6	8	12	24
Continued CRU confinement	→	→	→	→	→	→	→	→	→
12-Lead ECG ^b	X	X	X	X	X	X	X	X	

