Supine blood pressure ^c and pulse rate	X	X	X	X	X	X	X	X	
Orthostatic blood pressure, respiratory rate and oral temperature	X				X		X		
Serious and nonserious adverse event monitoring	→	→	→	→	→	→	→	→	→
Study intervention administration ^d	X								
Safety laboratory ^e	X ^g						X		
Lactate ^f	X ^g						X		
EPO (Day 7 and 14 only) ^f	X								
Reticulocytes (Day 7 and 14 only) ^f	X								
Ferritin & C reactive protein (Day 14 only)	X								
Pharmacokinetic	X	X	X	X	X	X	X	X	
CCI [REDACTED]	[REDACTED]	[REDACTED]	[REDACTED]	[REDACTED]	[REDACTED]	[REDACTED]	[REDACTED]	[REDACTED]	
p20 and p50	X						X		
Urinalysis (and microscopy, if needed)	X ^g								
Urine blank (Day 1 only)	X								
CCI [REDACTED]	[REDACTED]	[REDACTED]	[REDACTED]	[REDACTED]	[REDACTED]	[REDACTED]	[REDACTED]	[REDACTED]	

a. **0 H:** Predose sample collection.

b. **12-lead ECG:** Triplicate supine measurements.

c. **Supine blood pressure:** Where orthostatic blood pressure assessment will be conducted, supine blood pressure does not need to be repeated separately.

d. **Study Treatment Administration:** Refer to [Section 5.3.1](#) and [Section 6.1.1](#).

e. **Safety laboratory:** Participants should fast for at least 4 hours prior to sample collection, except 8 hours postdose samples. Only chemistry panel is required for 8 hours postdose samples.

f. **Lactate, EPO, Reticulocytes:** Unless needed for screening, review of data is not required prior to dosing but lactate and EPO data up to at least Day 7, and reticulocyte data up to at least Day 14 will be reviewed prior to dose escalation, and cumulative results will be reviewed as they become available. Refer to [Section 6.6.1](#).

g. **Safety laboratory and lactate 0 H:** For Day 7 and 14 only.

D. Part 3 SoA

Visit Identifier ^a	Screening	Period 1 to Period 4 ^b											F/U Contact ^c	E/T	
Days Relative to Day 1	Day -28 to Day -2	Day -1	Day 1						Day 2		Day 3	Day 4	Day 5	28-35 Days	
Hours After Dose			0 ^d	0.5	1	2	5	8	12	24	36	48	72	96	
Informed consent	X														
CRU confinement		X	→	→	→	→	→	→	→	→	→	→	→	X	
Inclusion/exclusion criteria	X	X ^k													
Medical/medication history	X														
Demography	X														
Physical exam (height and weight at Screening, only) ^e	X	X												X	
12-Lead ECG ^f	X		X			X	X	X	X		X		X	X	
Supine blood pressure and pulse rate	X		X		X	X	X	X	X		X		X	X	
Respiratory rate and oral temperature			X							X			X		
Contraception check	X	X											X	X	

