To better understand and guide formulation development for future clinical studies, preliminary assessment of a tablet formulation and examination of different particle size is also planned.

Since the dose in this Part (refer to [Section 4.3.3.3](#)) will be selected based on observed safety and tolerability of single doses in Part 1 and the dose selected will be lower than the highest dose tested in Part 1, standard safety monitoring will be used in this part of the study, without placebo control, and without on-site visit following discharge.

For all parts of the study

Considering the nonclinical safety studies with PF-07059013 in mice and dogs (see [Section 2.2.3](#)), the standard safety assessments used by the sponsor in trials administering investigational product for the first time to humans are deemed suitable (see [Appendix 2: Clinical Laboratory Tests](#)). In addition to the standard safety assessments, levels of lactate (Part 1 to 3), EPO and reticulocyte count (Part 2 only) will also be monitored to evaluate the potential risk of reduction in tissue oxygen delivery per unit volume of blood, for this class of mechanism. Due to the long half-life of RBC and lag for EPO stimulation, any potential effects on reticulocyte count and EPO will likely only manifest after a sustained period, hence assessments are planned for Part 2, from Day 7 onwards for EPO and reticulocyte count. Ferritin levels and respiratory rate will be also assessed based on non-adverse findings in the nonclinical studies with PF-07059013 (see [Section 2.2.3](#)), with ferritin assessment planned on/after Day 5 due to physiologic rationale that this is likely the earliest point at which modulation of ferritin could be detected.

To ensure that participants with undiagnosed hematological conditions and elevated baseline lactate are not enrolled, hemoglobin, reticulocyte count (Part 2 only), lactate, PT/INR and aPTT levels will also be assessed at screening.

To further permit assessment of modulation of oxygen affinity and possibly limit excessive pharmacological effect, measures of hemoglobin oxygen affinity (p20 and p50) will be

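### Part 2 escalation can be decided before the Day 14 EPO and lactate results that could complete the p50 stopping rule

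*Protocol*

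**What the plan says.** Protocol section 6.6.1 terminates escalation if p50 drops below 20 mmHg in two or more active participants at a dose level, "in association with one or more of the following, in any of the respective participants". In Part 2 the listed findings are EPO above the reference range, an absolute reticulocyte rise of at least 250,000/µL, and lactate above the upper limit of normal, each treatment emergent. Section 2.3.1 names this rule as a mitigation for tissue hypoxia.

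The same section sets the Part 2 minimum for each escalation: "review of EPO and lactate data up to at least Day 7, reticulocyte and p50 data up to at least Day 14", the remaining safety data to Day 15, and PK to Day 8, in at least 5 of 6 active participants and at least 1 on placebo. Footnote h of Table B and footnote f of Table C in section 1.3 repeat the split: "lactate and EPO data up to at least Day 7, and reticulocyte data up to at least Day 14 will be reviewed".

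Two provisions work the other way. Progression comes "after satisfactory review of the available safety and PK data", and Table C footnote f adds that "cumulative results will be reviewed as they become available".

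On timing, section 4.2 says that "any potential effects on reticulocyte count and EPO will likely only manifest after a sustained period". It gives this as the reason for starting both assessments at Day 7 of Part 2. Table C schedules "EPO (Day 7 and 14 only", predose, within its three intensive days.

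**The concern.** The rule is a conjunction. A low p50 does not trigger it without a correlate, so the correlates need to be looked at over the same span as p50. In Part 2 one of the three is (reticulocytes) and two are not (EPO and lactate). In Part 1 the two markers that apply, lactate and p50, share one cut at 8 hours.

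For EPO the split also sits uneasily with section 4.2, which describes the same lag for EPO and reticulocytes. Reticulocytes are nevertheless required to Day 14 and EPO only to Day 7, with no reason given for the difference.

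At stake is the release of the next, higher dose while a result that meets a named first-in-human stopping rule is still at the laboratory. The result could still end escalation when it arrived, but possibly after the next cohort had been dosed.

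**Working it through.** The plan has no figure to reproduce here, so the check sets the texts side by side and counts what falls between them.

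**Step 1. Cut-offs against the schedule.** The Day 14 draws are from Table C and the minimum cuts from section 6.6.1.

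| Marker | Role in the rule | Day 14 draws | Minimum cut |
|---|---|---|---|
| p50 | trigger | 0 h, 8 h | Day 14 |
| Reticulocytes | correlate | 0 h | Day 14 |
| EPO | correlate | 0 h | Day 7 |
| Lactate | correlate | 0 h, 8 h | Day 7 |

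EPO and lactate are cut 14 − 7 = 7 days before p50. The Day 15 requirement for the remaining safety data does not bring them back in, because the sentence names them separately and both footnotes repeat Day 7.

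**Step 2. What the minimum contains.** On-treatment EPO by Day 7 is the Day 7 predose value only, so 1 per participant, after 6 doses. Lactate is better covered: Table C alone gives Day 1 at 8 h and Day 7 at 0 h and 8 h, so at least 3.

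**Step 3. Results exposed.** Per participant: 1 EPO (Day 14, 0 h) + 2 lactate (Day 14, 0 h and 8 h) = 3. For the minimum set of 5 active participants: 5 × 1 = 5 EPO and 5 × 2 = 10 lactate. Day 10 lactate is left out: it is drawn 5 days before Day 15 and is very likely in hand.

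**Step 4. When the gap opens.** Day 15 safety data are awaited, so the decision cannot precede Day 15, 0 h (24 h after the last dose). The Day 14 EPO and first lactate are by then 24 − 0 = 24 h old, and the second lactate 24 − 8 = 16 h old. A result can be pending only if its turnaround exceeds those times. The documents give no turnaround for EPO or lactate.

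**Step 5. Is drug accumulation the reason to look later?** Fraction of steady state = 1 − 2^(−t/half-life). With 41 h, the longest predicted effective half-life in section 4.3.1 (for 3000 mg):
- Day 7 predose, t = 6 × 24 = 144 h: 1 − 2^(−144/41) = 0.91.
- Day 14 predose, t = 13 × 24 = 312 h: 1 − 2^(−312/41) = 0.995.

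The kinetics are predicted to be non-linear, so this is a rough guide. It suggests that the case for Day 14 rests on the biological lag in section 4.2 rather than on accumulation. That lag is stated for EPO and reticulocytes, not for lactate.

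**Step 6. Can Day 14 reticulocytes stand in for EPO?** Section 5.2 excludes screening counts above 150,000/µL in Part 2. A participant starting at that ceiling would need 150,000 + 250,000 = 400,000/µL, a 400,000/150,000 = 2.7-fold count, and a lower baseline needs a larger fold rise. EPO has only to cross its upper limit. The required correlate therefore cannot be assumed to cover the missing one.

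**Step 7. Where it would matter most.** Table 2 projects maximum Hb coverage of 7.4%, 22% and 45% at 600, 1200 and 2000 mg QD. The steps are 22/7.4 = 3.0-fold and 45/22 = 2.0-fold. The second passes the approximately 40% that section 4.3.3 says was previously studied in healthy adults. This is context for the consequence and does not measure the gap.

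**The case against.** The Day 7 minimum appears in section 6.6.1 and in both footnotes without contradiction, so it looks deliberate. Section 4.2 uses the lag to justify assessing EPO from Day 7 onwards, and nothing in the documents shows that a Day 7 EPO is uninformative. On Day 7 itself, p50, EPO and lactate are all sampled. Available results must be reviewed, the sponsor reviews unblinded data in real time (sections 6.3.2 and 9.5), the team may halt for other findings, and the sponsor cannot overrule an investigator who decides to stop. A missed trigger needs several things together: two or more p50 values below 20 mmHg, no qualifying correlate in hand, a first rise in exactly the pending sample, and no discretionary halt on p50 values already known to be low. A blanket Day 14 requirement would also delay escalations in which no p50 is below 20 mmHg and this rule cannot fire.

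Most of this stands and limits the weight of the point. It does not close the gap. Review of available data, and cumulative review as results arrive, do not oblige anyone to wait for a pending result. A discretionary halt is not equivalent to the stated rule that section 2.3.1 relies on. The last objection bears on the form of the fix.

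A reader might infer that the plan lets the team disregard Day 14 EPO and lactate, or that the stopping rule itself lapses at Day 7. It does neither: the criterion has no day limit, and any result in hand counts. A reader might also infer that an unsafe escalation is likely. The documents give no turnaround and no expected change between Days 7 and 14, so no probability can be attached.

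**Conclusion.** The mismatch is real and narrow. Escalation in Part 2 can properly proceed under the written minimum while a Day 14 EPO or lactate result that would complete the p50 rule is pending. The exposure is 3 results per participant, or 5 EPO and 10 lactate for the smallest permitted decision set. These are counts of unreviewed results, not a risk.

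The point is mainly about EPO: one on-treatment value within the minimum, at the first planned post-dose time, for a marker that the protocol expects to respond late. For lactate the lag argument is absent and earlier sampling is fuller, so the case there is consistency with p50.

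The conclusion assumes that the Day 14 samples are drawn as in Table C and that at least one result takes longer than the 24 h (EPO, first lactate) or 16 h (second lactate) that the decision already allows. If turnaround is shorter, the gap does not open in practice. This is a cheap improvement to a named safety rule. It does not show the escalation plan to be unsafe, or the Day 7 cut to be a drafting error.

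**What to change.** Add a condition to the Part 2 escalation paragraph of section 6.6.1, and mirror it in Table B footnote h and Table C footnote f: if two or more actively treated participants at a dose level have any post-treatment p50 below 20 mmHg, escalation will not proceed until the Day 14 EPO and lactate results for those participants have been reviewed.

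A simpler alternative is to extend the EPO and lactate minimum from Day 7 to Day 14 for everyone. It is easier to apply but holds every Part 2 escalation, including those in which this rule cannot fire. The conditional version waits only where it can. With exactly two such participants, that is 2 × 1 = 2 EPO and 2 × 2 = 4 lactate results. If only one marker is extended, it should be EPO.

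The cost is a protocol amendment to one paragraph and two footnotes, with IRB/EC approval under section 10.1.1, and a possible wait for results. The length of the wait is unknown, because turnaround is not stated. No samples or visits are added: the EPO is drawn with the Day 14 predose reticulocytes and p50, and lactate at the two Day 14 p50 time points, all of which are already awaited.

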6.7. Intervention After the End of the Study

No intervention will be provided to study participants at the end of the study.

7. DISCONTINUATION OF STUDY INTERVENTION AND PARTICIPANT DISCONTINUATION/WITHDRAWAL

7.1. Discontinuation of Study Intervention

In rare instances, it may be necessary for a participant to permanently discontinue study intervention (definitive discontinuation). Reasons for definitive discontinuation of study intervention include the following: withdrawal of consent by the participant, SAE or clinically significant finding that impacts safety of participant per PI judgement, death, protocol deviation impacting study data or integrity, study terminated by study sponsor.

Note that discontinuation of study intervention does not represent withdrawal from the study. If study intervention is definitively discontinued, the participant will remain in the study to be evaluated at the early termination/discontinuation visit. See the [Schedule of Activities](#) for data to be collected at the time of discontinuation of study intervention and follow-up for any further evaluations that need to be completed.

In the event of discontinuation of study intervention, it must be documented on the appropriate CRF/in the medical records whether the participant is discontinuing further receipt of study intervention or also from study procedures, posttreatment study follow-up, and/or future collection of additional information.

ECG Changes

A participant who meets either bulleted criterion based on the average of triplicate ECG readings will be withdrawn from the study intervention.

- QTcF >500 msec.
- Change from baseline: QTcF >60 msec.

If a clinically significant finding is identified (including, but not limited to, changes from baseline in QTcF after enrollment), the investigator or qualified designee will determine if the participant can continue in the study and if any change in participant management is needed. This review of the ECG printed at the time of collection must be documented. Any new clinically relevant finding should be reported as an AE.

Potential Cases of Acute Kidney Injury

Abnormal values in SCr concurrent with presence or absence of increase in BUN that meet the criteria below, in the absence of other causes of kidney injury, are considered potential cases of acute kidney injury and should be considered important medical events.

An increase of ≥ 0.3 mg/dL (or ≥ 26.5 μ mol/L) in SCr level relative to the participant's own baseline measurement should trigger another assessment of SCr as soon as practically feasible, preferably within 48 hours from awareness.

If the second assessment (after the first observations of ≥ 0.3 mg/dL [or ≥ 26.5 μ mol/L] in SCr relative to the participant's own baseline measurement) is ≥ 0.4 mg/dL (or ≥ 35.4 μ mol/L), the participant should be discontinued from the study and adequate, immediate, supportive measures taken to correct apparent acute kidney injury.

Participants should return to the investigator site and be evaluated as soon as possible, preferably within 48 hours from awareness of the second assessment confirming abnormal SCr result. This evaluation should include laboratory tests, detailed history, and physical assessment. In addition to repeating SCr, laboratory tests should include serum BUN, serum creatine kinase, and serum electrolytes (including at a minimum potassium, sodium, phosphate/phosphorus, and calcium), in addition to urinary dipstick, urine microscopic examination, and urinary indices. All cases confirmed on repeat testing as meeting the laboratory criteria for acute kidney injury, with no other cause(s) of laboratory abnormalities identified, should be considered potential cases of drug-induced kidney injury irrespective of availability of all the results of the investigations performed to determine etiology of the abnormal SCr. If ≥ 2 healthy participants in a given period/treatment arm are noted to have 2 consecutive SCr results of ≥ 0.3 mg/dL (or ≥ 26.5 μ mol/L), an assessment of whether the finding may be considered an adverse drug reaction should be undertaken.

